1 STUDY INFORMATION

1.1 Full/Long Title of the Study

A clinical investigation of an autonomous phone conversational agent for cataract surgery follow-up

1.2 Short Study Title

Autonomous telephone follow-up after cataract surgery

1.3 Protocol Version Number(s) and Date(s)

| .0 | Initial draft | 10 November 2020 |
|-----|---|------------------|
| .1 | Pre-IRAS format submission draft | 19 January 2021 |
| .2 | Updated to reflect feedback from trial team | 2 February 2021 |
| .3 | Revisions from joint call with trial team | 22 February 2021 |
| .4 | Minor revisions | 23 February 2021 |
| .5 | Minor revisions | 30 March 2021 |
| .6 | Sponsor feedback revisions | 27 April 2021 |
| .7 | Minor revisions | 14 May 2021 |
| 1.0 | Submission version | 17 May 2021 |

1.4 Research Reference Numbers

| IRAS Number: | 297548 |
|--------------------|---------------|
| SPONSORS Number: | 21WE6780 |
| NIHR Award Number: | AI_AWARD01852 |

4 ABBREVIATIONS AND KEY TERMS

| Table 2. Abbreviations | | |
|----------------------------|--|--|
| Abbreviation / Key Term | Full Phrase / Definition | |
| AHSN | Academic Health Science Network | |
| AI | Artificial Intelligence | |
| BRC | Biomedical Research Centre | |
| CONSORT | Consolidated Standards of Reporting Trials | |
| DPA 2018 | Data Protection Act 2018 | |
| EHR | Electronic Health Record | |
| FAQ | Frequently Asked Question | |
| GDPR | General Data Protection Regulation | |
| GIRFT | Getting It Right First Time programme | |
| ICORG | Imperial College Ophthalmology Research Group | |
| Imperial | Imperial College Healthcare NHS Trust | |
| NASSS | Non-adoption, Abandonment, Scale-up, Spread, and Sustainability framework | |
| NHS | National Health Service | |
| NOD | National Ophthalmology Database | |
| NPS | Net Promoter Score | |
| Oxford | Oxford University Hospitals NHS Foundation Trust | |
| PERC | Patient Experience Research Centre | |
| PPI | Patient and Public Involvement | |
| SPIRIT-AI | Standard Protocol Items: Recommendations for Interventional Trials - Artificial Intelligence | |
| sus | System Usability Scale | |
| TUQ | Telehealth Usability Questionnaire | |
| Ufonia | Ufonia Limited (Company Number: 10692039) | |

5 STUDY SUMMARY

Table 3. Study Summary

| Table 3. Study Summary | |
|--------------------------|--|
| Study Title | A clinical investigation of an autonomous phone conversational agent for cataract surgery follow-up |
| Short title | Autonomous telephone follow-up after cataract surgery |
| Study Design | The study will be a multi-centre, mixed-methods clinical investigation to develop evidence regarding the feasibility, acceptability and potential effectiveness of DORA . |
| Study Participants | The study will include adults (aged 18 years or older) who are on the waiting list for either their first or second eye cataract surgery at Oxford or Imperial. To be eligible, the patients must have no history of significant ocular comorbidities and have a routine surgery with no intraoperative complications. |
| Planned Size of Sample | The planned sample size is 591 patients, split mostly equally between Oxford and Imperial clinical sites (see Table 1 for details on how this estimate was produced). |
| Follow up duration | Imperial: patients will receive the standard face-to-face appointment within a few days of having the autonomous call (dependent on current Covid-19 restrictions). |
| | Oxford: there will be no face-to-face follow-up for patients at the Oxford site as this is the standard of care. |
| | At both sites, an additional 3-month follow-up period where unplanned eye-related clinical visits will be recorded and assessed. |
| Planned Study Period | The total duration of the study will take up to 3 years, including the recruitment of patients, intervention refinement period, main intervention period, and analysis of results. |
| Research Question/Aim(s) | The aim of the study is to assess the evidence for the safety of using DORA to deliver autonomous cataract surgery follow-up assessments. This ability will be evaluated in comparison to an expert human clinician to assess the research question: Can DORA identify which patients need clinical follow up after a cataract operation? |

5.2 Role of Study Sponsor and Funder

This study is funded by an NIHR Artificial Intelligence in Health and Care Award granted to Ufonia. Ufonia distributes on behalf of NIHR funding to Imperial College London, the University of Plymouth and the University of Oxford for this study execution. This funding arrangement is governed by a consortium agreement which defines Imperial College London as being responsible for the study design, conduct, data analysis and interpretation, manuscript writing, and dissemination of results in collaboration with the academic consortium including the University of Plymouth and the University of Oxford. Whilst Ufonia has contributed and reviewed the study design and will support the trial in providing technology support, the academic collaboration, led by Imperial College London, is solely responsible for the study execution and dissemination of results to assure an independent assessment of Ufonia's technology. The academic consortium maintains a free and independent unrestricted right of publication of the study's findings as to avoid any conflict of interest.

5.3 Roles and Responsibilities of Study Management Committees/Groups and Individuals

A study steering board composed of the Chief Investigator, Principal Investigators, Co-Investigator, a member of the public, Ufonia's CEO, Ufonia's Medical Director and an external researcher (from the study) will meet every two months to review progress against the protocol to provide study governance and oversight. Reports shall be distributed for review by the study team for action.

Ufonia will appoint a Patient and Public Involvement (PPI) committee. With input from the Imperial College Patient Experience Research Centre (PERC), the Oxford University Academic Health Science Network (AHSN) and based on NIHR Involve guidance, a term of reference, confidentiality agreement and a background assessment form to Ufonia to structure the aims of the PPI group. Membership of this Ufonia PPI group is voluntary but requires members to be committed to attend meetings and to respond to emails/correspondence. The initial term of membership is for the duration of the study from early in the preparation phase (March 2021). Further details about PPI are included in the study protocol (see section 9.4).

5.5 Keywords

Artificial Intelligence (MeSH), Natural Language Processing (MeSH), Telemedicine (MeSH), Cataract (MeSH), Aftercare (MeSH), Speech Recognition Software (MeSH)

6 STUDY FLOW CHART

Patients receiving usual care for cataract surgery typically progress through four stages. Participants in this study will undergo two additional stages that are specific to the study (stages 4 and 6). There are six stages that participants of the study will potentially go through. These stages, and their approximate timeline, are visualised in the flow diagram below (Figure 1).

- 1. Stage 1. The patient is referred by a clinician for cataract surgery.
- 2. Stage 2. The patient's suitability for surgery is determined at a pre-assessment appointment or a one-stop cataract clinic. Patients who meet the eligibility criteria for the study at this stage will be provided with a participant information sheet (see 13.1 Appendix 1) and, if they are willing to participate, informed consent will be collected (see 13.2 Appendix 2).
- 3. Stage 3. The patient undergoes their scheduled cataract surgery. If the surgery was uncomplicated, a patient may also consent to participate in the study in the recovery lounge.
- 4. Stage 4. If the patient is consented to participate in the study, they will receive a follow-up call from DORA (supervised by a clinician). The call script used by DORA will be reviewed by supervising PIs in advance in order to reduce incidence of non-compliance through misunderstanding.
- 5. Stage 5. If the patient had the surgery at Imperial, regardless of whether or not they are participating in the study, they will have a scheduled follow-up with a clinician.
- 6. Stage 6. If the patient consented to participate in the study, they may be randomly selected to participate in a semi-structured interview, to provide more in-depth feedback about their experience using **DORA**.

Figure 1. Participant flow diagram

The patient flow described above reflects the delivery stage of the study (see Figure 2). Before delivery begins, the first part of the study will be dedicated to obtaining the necessary ethical approvals, NHS contracts, and technical capabilities to deliver the intervention. These steps are captured in the project management, technical, and evaluation work packages (see WPs 1, 2, and 4 in Figure 2). Participant recruitment will begin approximately one month before data collection, with Imperial starting recruitment and delivery two months before Oxford (see WPs 3a and 3b in Figure 2). Prior to the main intervention period, a 4-week intervention refinement period will be conducted to identify any issues and make adjustments to the intervention execution. The final six months of the study will see the completion of data collection and will focus on conducting the evaluation, and reporting results for publication (see WPs 1, 4, and 5 in Figure 2).

Figure 2. High-level study gantt chart

7 INTRODUCTION

7.1 Background

The UK's ageing population is causing an increased demand for healthcare services that is exceeding clinical capacity [1]. Demand has been further exacerbated by the Covid-19 pandemic, as the widespread cancellation of elective care has created a large backlog of clinical work [2]. However, a large proportion of this clinical work is taken up by highly repetitive and low skill tasks. Therefore, there is a need to improve efficiency in the delivery of care, and to collect data that can be analysed to support routine improvement and optimisation, through the automation of routine clinical interactions.

One area of care where improved efficiency is urgently needed is cataract surgery. Cataract surgery is already the most common operation in the NHS, with approximately 450,000 procedures conducted per year [3]. Covid-19 has caused record delays in receiving planned surgeries [4], and average wait times for cataract surgery were already approximately 2.5 months [5]. The ageing population will also have a significant impact on the number of patients with cataracts, which is expected to double between now and 2050 [6]. The cataract pathway is also an ideal case for optimisation because there is little variability and high levels of patient safety; the most significant postoperative complication (endophthalmitis) occurs in fewer than 1 in 1,000 cases [7]. To address this clinical need, an innovative solution is required.

7.2 Rationale

Like most operations, cataract surgery requires a post-operative check to monitor for complications and assess success. This has historically been performed with a face-to-face visit; prior to the Covid-19 pandemic, this was standard procedure for 72% of NHS Trusts [8]. However, this post-operative system has a high operational demand and is not always necessary; a recent ophthalmology Getting It Right First Time (GIRFT) report stated that a hospital review of cataract surgery patients is not required, if alternative follow-up arrangements are in place [8]. In the current context of the Covid-19 pandemic, face-to-face visits also pose a high risk for virus transmission due to the proximity of patient and clinician. This is reflected in the latest guidance from GIRFT and the Royal College of Ophthalmologists on restarting cataract surgery during the pandemic which recommends that patients should not be followed up in hospital after routine uncomplicated cataract surgery and should instead receive a telephone consultation or review with their local optometrist [9].

The solution developed to improve clinical efficiency for cataract surgery follow-up is a natural language, voice telemedicine conversation delivered to patients via telephone call (**DORA**, Ufonia). Since Ufonia's conception in 2016, several grants and partnerships have supported **DORA's** development and pilot testing at Buckinghamshire Healthcare NHS Trust (BHT), Department of Ophthalmology. For the patient, this is intended to be no different than a regular telemedicine consultation with a doctor or nurse; it does not require the download of an app, the provision of a device, or any training. This is important because the populations that consume the majority of healthcare services (elderly and socio-economically disadvantaged) tend to be relatively more digitally disenfranchised [10].

The solution potentially has several benefits for patients and healthcare staff, which will be evaluated in the study [11]. For patients, **DORA** will provide a reliable, consistent safety-net after surgery. Patients will be able to ask questions about their recovery from the convenience of home. Reducing the number of in-person follow-ups will also benefit clinicians by enabling them to spend their time on higher-value clinical activities, making patients more likely to receive timely care for their initial cataract surgery or for other conditions. In addition, telephone follow-up reduces the risk of Covid-19 transmission and frees up hospital space to help meet the increasing patient demand. Whilst this study focuses on cataract surgery follow-up, the underlying platform will be applicable to a wide range of routine clinical tasks. The need for an effective automated tool is especially great as a 'new normal' of widespread remote clinical care is established in the wake of Covid-19.

7.3 Theoretical Frameworks

Two complementary frameworks were used to support the conception and development of the study plan by ensuring that a holistic set of variables were included in the evaluation [12,13]. Several quantitative analyses will be conducted to achieve the study's objectives; including comparing the agreement of **DORA's** and the supervising clinician's decisions and using validated questionnaires to evaluate **DORA's** usability [14,15]. Qualitative analysis will be completed by semi-structured interviews with a subset of users structured according to the Theoretical Framework of Acceptability [16]. The use of both quantitative and qualitative methods to evaluate usability will enable the data to be triangulated.

These three frameworks and two scales will form the theoretical basis for the evaluation of **DORA**:

- 1. Assessment of Health Information Technology Interventions in Evidence-Based Medicine Evaluation Framework [12]. This framework was chosen to help structure the study evaluation because it includes a holistic set of outcomes, including safety, privacy, appropriateness, and cost-effectiveness.
- Long-term adoption and suitability to further trials will be evaluated using the Non-Adoption, Abandonment and Challenges to the Scale-up, Spread and Suitability (NASSS) framework [13]. This framework is important to include because interventions can only add value if they are successfully adopted and used. This framework emphasises the consideration of the multiple levels - individuals and systems - that influence adoption and non-adoption.
- 3. The Theoretical Framework of Acceptability (TFA) will be used to structure the semi-structured interview guide [16]. This framework was chosen because it was developed specifically for health interventions, captures a multi-faceted view of acceptability (with seven components), and emphasises the importance of considering different time points when evaluating acceptability [16].
- 4. The System Usability Scale (SUS) [14]. The SUS is one of the most widely-adopted measures of usability and is still recommended for use after several decades of use [17].
- 5. The Telehealth Usability Questionnaire (TUQ) [15]. In addition to the SUS, the TUQ will be used in the study because it was developed recently and focuses specifically on modern telehealth interactions. It has been demonstrated to be a reliable measure of the quality of telehealth technologies.

7.4 Research Question

DORA was developed to provide an alternative for conducting post-cataract surgery follow up assessments to save nurses' and other clinicians' time. The key outcome of this study is evaluating **DORA's** ability to accurately identify which patients have postoperative complications which would justify specialist care, and assessing **DORA's** accuracy compared to an expert clinician. To assess this critical capability, the research question that this study will investigate is: Can **DORA** identify which patients need clinical follow up after a cataract operation?

7.5 Aims and Objectives

The purpose of this clinical investigation is to evaluate the safety, usability, acceptability, efficacy, and cost-effectiveness of Ufonia's autonomous cataract follow-up call system (**DORA**) at detecting patients that require further assessment. The aim is to establish preliminary safety evidence by examining the level of agreement between **DORA** and the supervising clinician on symptom and overall management plan decisions. Therefore, the focus will be on patients undergoing routine surgery. In order to achieve these aims, there are several objectives (see Figure 3):

- 1. To evaluate the level of agreement between **DORA** and an expert human clinician and identify any factors that affect that level of agreement;
- 2. To establish baseline rates of sensitivity and specificity for **DORA's** detection of patients that have postoperative complications;
- 3. To evaluate **DORA's** feasibility; i.e. whether **DORA** can engage with patients enough to produce sufficient data to perform an accurate assessment;
- 4. To evaluate the usability of an autonomous call, in comparison with existing standards of care, explore patient perceptions about whether DORA is acceptable, appropriate, satisfactory and evaluate cost-effectiveness of autonomous calls in comparison with existing standards of care.

Figure 3. Logic diagram of the study

8 METHODS

8.1 Trial Design

Using an implementation science construct, the study will use mixed methods. Quantitative methods will be examining the inter-rater reliability between **DORA** and the supervising clinician for assessments of symptoms and management plan decisions. Usability will also be assessed using validated, quantitative questionnaires. Qualitative methods using semi-structured interviewing will also assess **DORA's** usability, acceptability, satisfactoriness, and appropriateness to collect more in-depth feedback and explore **DORA's** strengths and weaknesses. The development of the protocol incorporated the guidelines from the SPIRIT-AI checklists (see 13.3 Appendix 3) [18]. Public Health England's guidance summaries for evaluation in health and well-being were also consulted when developing the protocol [19].

The study will last up to three years: the first year will be focused on evaluation and intervention refinement, including a 4-week trial of the intervention execution to identify any adjustments needed; this will be followed by the study implementation and follow-up; and the last several months will be dedicated to post-evaluation analysis and write-up.

8.1.1 Timeline

The study may last up to three years with **DORA** calls taking place over a six- to twelve-month period at both clinical sites to enable sufficient flexibility to meet the recruitment targets. Recruitment will begin approximately one month before the start of call delivery at both sites, but the start dates for the two sites may be staggered. Call delivery will last for approximately a year after recruitment. For both sites, recruitment will stop approximately 6 weeks prior to the end of the call delivery period. This timeline assumes return to elective surgery; any changes due to COVID-19 will require amendment. The overall study timeline is summarised in Figure 4.

| Year | Year 1 | Year 2 | Year 3 |
|--------------------------------|--------|--------|--------|
| WP3a: Clinical (Imperial) | | | |
| Intervention refinement period | | | |
| Recruitment | | | |
| Call delivery | | | |
| WP3b: Clinical (Oxford) | | | |
| Intervention refinement period | | | |
| Recruitment | | | |
| Call delivery | | | |

Figure 4. Overall call delivery timeline

8.2 Study Context

8.2.1 Participants

Patients who are listed for routine cataract surgery at either Imperial or Oxford NHS Trusts are eligible for this study.

8.2.2 Setting

This is a multi-centre study incorporating two NHS academic teaching hospitals - Imperial College Healthcare NHS Trust and Oxford University Hospitals NHS trust.

The management of the intervention (**DORA**) is accessible through any web-browser and investigators will be provided with secure log in.

8.2.3 Intervention(s)

DORA uses a variety of AI technologies to deliver the patient follow-up call, including: speech transcription, natural language understanding, a machine-learning conversation model to enable contextual conversations, and speech generation. Together, these technologies cover the input, processing and analysis, and output needed to maintain a natural conversation. **DORA** is configured to deliver calls through a telephone connection as a real-time, stand-alone system: the operator inputs individual patient details to initiate the call and completes a summary in the electronic health record (EHR) afterwards. The call that patients will receive from **DORA** will include several conversational elements:

- Greeting and introduction
- Identification of patient
- Cataract follow-up questions
- Patient's queries
- (Decision)
- Questions about acceptability
- Closure of call

The entire conversation will be supervised by a clinician. This clinician will be able to interrupt the call at any point if the system fails, the patient struggles to interact with it, or **DORA** does not collect sufficient information from the patient. The call will proceed in the following stages (visualised in Figure 5):

- 1. Stage 1. Call initiation: the supervising clinician will confirm the suitability of the patient, input their details, and initiate the call.
- 2. Stage 2. Symptom assessment: Once the call has begun, **DORA** will verify the identity of the patient and proceed through the cataract follow-up questions. As the patient answers the questions, both **DORA** and the supervising clinician will record their independent assessment about the clinical significance of the symptoms elicited.
- 3. Stage 3. Management plan decision: Once all of the follow-up questions have been asked, **DORA** and the supervising clinician will independently make and record their decisions about the management plan for the patient. **DORA** will then inform the patient of the clinician's decision about their management plan (i.e. whether specialist review is required or not).
 - Stage 3a: Optionally, if required, the supervising clinician can ask additional clarifying questions.

Figure 5. Flow Diagram of DORA's call with patient

8.2.4 Comparator(s)

Imperial sees all of their post-operative cataract patients at a face-to-face out-patient appointment with an ophthalmologist or specialist nurse. This is conducted between three to four weeks following the procedure. Therefore, patients at Imperial will receive their call from **DORA** within 3 days before their scheduled appointment (day 25-27 post-surgery). This will enable the results of the **DORA** call to be compared with the face-to-face appointment at Imperial to assess whether any complications were correctly identified and if the management plan remains the same.

For patients at both clinical sites, health records will be examined 90 days after the call to determine if the patient presented to an eye clinic with any complications from surgery. This comparison of the follow-up with actual complication rate will enable an assessment of **DORA's** safety (see Table 6).

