8.2.5.2 Secondary Outcomes

There will be several secondary outcome measures to assess the clinical safety, feasibility, usability, and acceptability of the system (see Table 6).

Clinical safety

To examine safety, two outcomes will be captured. Firstly, patients at both sites will have a retrospective case review of both general and ophthalmic electronic health records at 90 days after their initial operation. Complications will be identified from patient's medical records related to any unplanned eye-related clinical episode.

Secondly, all cataract surgery patients at Imperial were historically followed up face-to-face between 3-4 weeks post-surgery in a dedicated post-op clinic. Any complications requiring a change in patient management at slit lamp review or from attending eye casualty services (as the Oxford site does not normally perform face-to-face follow-ups) will be compared with the decisions made by **DORA** and the clinician. If Imperial changes their method of follow-up due to the COVID-19, assessment for complications will be done by checking hospital medical records as is done at the Oxford site.

Feasibility

Feasibility will be assessed by examining the proportion of autonomous calls that were completed without needing any intervention from the supervising clinician. All interruptions or clarifying questions of the supervised call will be logged; the supervising clinician will be asked to log the reason for asking clarifying questions. If clarifying questions were asked because the clinician felt that there was insufficient information for either individual symptoms or to make a management plan, the clinician's management plan before and after clarifying questions will be captured to see if clarifying questions changed the management plan.

Usability

Usability will be assessed using questions presented to patients following calls delivered by online and paper surveys distributed to participants. These questions will be drawn from the System

Usability Scale (SUS) and Telehealth Usability Questionnaire (TUQ; see 13.4 Appendix 4 for a sample survey) [14,15].

Acceptability, satisfaction, and appropriateness

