DORA's acceptability, satisfactoriness, and appropriateness will be assessed during qualitative interviews with a subset of the patients. These semi-structured interviews will provide an opportunity for patients to provide more in-depth feedback about what they liked about **DORA** and any barriers to use that they experienced during the call (see 13.5 Appendix 5 for a sample topic guide). The supervising clinician will also be asked to provide feedback about their level of satisfaction with the system and any safety concerns they might have.

Patients' willingness to recommend **DORA** to others will also be assessed at the end of the call [20]. **DORA** will calculate a net promoter score (NPS) by asking patients "on a scale of 1 to 10, how likely would you be to recommend this automated service to a friend or colleague." **DORA** will follow up by asking patients to "tell me why you gave that score."

Cost-effectiveness

Cost-effectiveness will be examined by collecting and analysing health economic data before and during the study. The costs of implementing **DORA** will be compared with historical data about the costs of the usual standard of care.

| Secondary Outcome | Outcome Measure | | | |
|-----------------------|---|--|--|--|
| Clinical Safety | Complications identified from patients' electronic health records up to 90 days following cataract surgery | | | |
| | Congruence between complications identified and management planned in DORA call and face-to-face follow up (Imperial) Comparison to data from patients attending eye casualty (Oxford) | | | |
| Feasibility | Proportion of autonomous calls that were completed without needing any intervention from the supervising clinician | | | |
| | Clinician-reported reasons for asking clarifying questions | | | |
| Usability | System Usability Scale (SUS) [14,17] | | | |
| | Telehealth Usability Questionnaire (TUQ) [15] | | | |
| | Qualitative feedback from semi-structured interviews | | | |
| Acceptability | Qualitative feedback from semi-structured interviews | | | |
| Satisfaction | Qualitative feedback from semi-structured interviews, Net Promoter Score (NPS) | | | |
| Appropriateness | Qualitative feedback from semi-structured interviews | | | |
| Cost-effectiveness | Comparison of the costs of implementing DORA and the costs of the usual standard of care | | | |
| Identify improvements | Synthesis of all of the outcome measures previously described | | | |

Table 6. Secondary Outcome Measurement

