8.3.4 Adherence

The **DORA** calls will be recorded and the study team will monitor the use of the technology and assure the system is being used within designed parameters during the study.

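### The printed Imperial call window, days 25–27, is the three days before a day-28 visit only, and falls wholly after any visit on day 24 or earlier

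*Protocol*

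**What the plan says.** Protocol section 8.2.4 says of Imperial's face-to-face appointment: "This is conducted between three to four weeks following the procedure". From this it derives the timing of the call: "within 3 days before their scheduled appointment (day 25-27 post-surgery"). It then gives the purpose, which is to check the call's findings and management plan against those of the appointment.

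Two other places give the order. The Study Summary (section 5, Table 3) says that at Imperial "patients will receive the standard face-to-face appointment within a few days of having the autonomous call". Section 6 puts the call at stage 4 and the visit at stage 5, where Imperial patients, "regardless of whether or not they are participating in the study, they will have a scheduled follow-up with a clinician".

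Table 6 in section 8.2.5.2 makes the comparison a clinical-safety measure: "Congruence between complications identified and management planned in DORA call and face-to-face follow up (Imperial"). The same section has a fallback: "If Imperial changes their method of follow-up due to the COVID-19, assessment for complications will be done by checking hospital medical records".

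Appendix 6, the October 2020 audit of Imperial's one-stop clinic, reports a mean of 24.33 days from surgery to first follow-up. It adds that an unstated number of patients were seen before day 21.

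**The concern.** Section 8.2.4 gives two instructions for the same call. One is relative to the patient's appointment; the other is a fixed range of days after surgery. With visits spread over days 21 to 28, one three-day range cannot be the three days before every visit. Staff who scheduled by the printed days would call some patients after their visit.

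The order matters because the visit is the yardstick for the call. If it comes first, a complication may already have been found and treated, and that patient no longer tests whether DORA would have picked it up. Such findings were not rare in the audit: Appendix 6 lists 7 patients whose management changed at follow-up, 6 of them for uveitis. The rate is uncertain. The audit line prints 21% beside 7/25, but 7/25 = 28%, and only 24 of the 25 attended.

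No stated check is aimed at this. Before each call, "the supervising clinician will confirm the suitability of the patient" (section 8.2.3), and the study team is to "assure the system is being used within designed parameters during the study" (section 8.3.4), but neither mentions whether the visit has taken place. The withdrawal rule in section 8.3.1.3 covers unplanned reviews, and appointments prompted by an abnormal operative course, before the call. It does not cover a routine visit that precedes the call.

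**Working it through.** **Inputs.** Visit day v: three to four weeks, so days 21 to 28 (section 8.2.4). Rule: call on days v−3 to v−1. Printed window: days 25, 26, 27. Audited mean visit: day 24.33 (Appendix 6).

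**Reproducing the printed window.** Set v−3 = 25 and v−1 = 27; both give v = 28. A day-27 visit gives 24–26 and a day-29 visit gives 26–28, so no other whole day reproduces it.

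**Where the printed days fall for each visit day.**

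| Visit day | Days the rule gives | Printed days before visit | Same day | After visit |
|---|---|---|---|---|
| 21 | 18–20 | 0 | 0 | 3 |
| 22 | 19–21 | 0 | 0 | 3 |
| 23 | 20–22 | 0 | 0 | 3 |
| 24 | 21–23 | 0 | 0 | 3 |
| 25 | 22–24 | 0 | 1 | 2 |
| 26 | 23–25 | 1 | 1 | 1 |
| 27 | 24–26 | 2 | 1 | 0 |
| 28 | 25–27 | 3 | 0 | 0 |

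Over days 21 to 28 the rule gives call days 18 to 27, against three printed days. A visit on day 20 would need a call on days 17–19.

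**Same-day calls.** If a call earlier on the day of the visit counts, the rule becomes v−3 to v. All three printed days are then also allowable for a day-27 visit, and day 25 becomes allowable for a day-25 visit. Nothing changes for visits on day 24 or earlier.

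**At the audited mean.** The rule gives 24.33 − 3 = 21.33 to 24.33 − 1 = 23.33, before the printed window opens. The printed days fall 25 − 24.33 = 0.67 to 27 − 24.33 = 2.67 days after that mean. The mean is 28 − 24.33 = 3.67 days short of the visit day that the window implies.

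**The other reading of the bracket.** If days 25–27 describe the appointment, calls fall on days 25 − 3 = 22 to 27 − 1 = 26 and the ordering conflict disappears. Appointments are then confined to three of the eight whole days in the stated range, and the audited mean lies outside them. The exact fit to day 28 makes this the less natural reading, and the text would still need correcting.

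**The case against.** The strongest reply is that the operative instruction is already clear. The main clause ties the call to the patient's own appointment, the stated purpose needs the call first, and sections 5 and 6 give the same order. A site that follows them misorders no calls, and the bracket may be no more than an example worked for a four-week visit. This stands, and it keeps the point small. It does not make the bracket harmless: it is printed as an operating figure, and for any visit on day 24 or earlier it cannot be followed together with the rule.

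The audit is also thin evidence about trial visits. It covers one month and 24 attended follow-ups, all from the one-stop clinic. Appendix 6 says the general pre-assessment pathways were not audited, and Table 7 expects 135 of Imperial's 286 recruits (135/286 = 47%) from there. The audit shows that visits before day 25 are plausible, not how common they will be.

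The SAP names no analysis of congruence between call and visit. It tabulates DORA's decision against three complication variables, one of them `unexpected-change-management`, without giving their sources. If that variable draws on the face-to-face visit, a patient treated there, then called and passed by DORA, would count as a false negative. If it does not, that table is untouched.

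A reader might infer that half of Imperial calls would follow the visit, because that happens on four of the eight visit days. The documents give no distribution of visit days, and the relative rule, if followed, yields none. A reader might also infer that the primary result is compromised. It is not: DORA and the clinician rate the same call, so that agreement does not depend on when the visit takes place.

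**Conclusion.** The inconsistency is real and minor. Read as call days, the printed window is the three days before a day-28 visit and no other, and it lies wholly after visits on day 24 or earlier. The share of calls affected cannot be computed and may be zero. Exposure is limited to the secondary Imperial comparison of the call with the visit, plus one SAP table if its variable includes visit findings. It arises only while Imperial keeps face-to-face follow-up.

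This rests on two assumptions: that the bracket gives call days, and that calls and visits are counted from surgery in the same way. Whether surgery is day 0 or day 1 then makes no difference to their order.

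**What to change.** In section 8.2.4, delete the bracketed day range and put no other fixed range in its place. State that the call is made no more than three days before the booked appointment, and always before it.

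In the Imperial comparison of DORA with the face-to-face visit (Table 6), include only patients whose call came before the visit. Keep same-day calls made before the visit, since they remain valid tests. Apply the same restriction to Imperial patients in the SAP's `unexpected-change-management` table if that variable draws on the visit, and state its source. Report the number excluded.

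The cost is one deletion and one check of dates, with times for same-day calls. Section 9.11 already provides for storing call metadata; the visit date comes from the patient's record. The downside is possibly a few fewer patients in one secondary comparison. If no call was misordered, nobody is excluded and the report shows it.
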